6. RADIATION THERAPY

6.1 Specifications for Radiation Therapy

SBRT/SABR will be delivered to up to three separate metastatic sites in 3-5 fractions. The primary lung tumor may be treated as well. Patients will receive the radiation therapy dose specified in **Table 2** for a given treatment site. Treatment at the protocol defined dosing regimen is only permitted if the normal tissue criteria are met. As a default dosing scheme, if dosimetric criteria are not achieved, then a dose of 30 Gy in 5 fractions will be delivered. A minimum of 95% of the prescribed dose must be delivered to the treatment planning volume (PTV). 90% will be considered an acceptable minor deviation.

The lesions selected for treatment should be lesions that can be safely irradiated with focal irradiation while sparing normal tissue in accordance with standard radiation oncology practice. If symptomatic or at risk lesions are present, these lesions should be prioritized for the target selection. No more than one lung lesion may be treated.

Table 2. Specified SBRT/SABR Prescription Doses

Lesion Location	Dose/Fractionation	Acceptable Variation
Lung-Peripheral Lesion	45 Gy/3 fractions	40 Gy/5 fractions
Lung-Central Lesion	50 Gy/5 fractions	40 Gy/5 fractions
Mediastinal/Cervical Node	50 Gy/5 fractions	40 Gy/5 fractions
Liver	45 Gy/3 fractions	40 Gy/5 fractions
Spine/Para-spinal	30 Gy/3 fractions	30 Gy/5 fractions
Bone (Other than spine)	30 Gy/3 fractions	30 Gy/5 fractions
Adrenal Gland/Pelvic Metastases	45 Gy/ 3 fractions	40 Gy/5 fractions

6.2 Radiation Therapy Simulation

All patients will undergo immobilized 1mm CT scans for treatment planning. IV contrast is required for central lung lesions and liver metastases. For other sites, the use of IV contrast is encouraged and left to the discretion of the treating radiation oncologist. Fiducials may be required for tumor tracking. Respiratory motion management (RMM) is required for all lesions for the potential for respiratory motion. Daily IGRT with CBCT is required for all treatment sites when an approved non-CyberKnife treatment system is utilized.

6.3 Treatment Planning and Target Volumes

Location: Each lesion will be assigned to one of the 7 locations specified in **Table 2**.

Lung Peripheral Lesion: The lesion is outside the proximal bronchial tree as defined as within 2cm in all directions around the carina, right and left main bronchi, right and left upper lobe

bronchi, intermedius bronchus, right middle lobe bronchus, lingular bronchus and right lower lobe bronchi. The lesion does not the mediastinal or pericardial pleura.

Lung Central: The lesion is within 2cm of the proximal bronchial tree.

Mediastinal/Cervical Node: The lesion arises in the anatomic mediastinum or cervical lymph node levels I-VI or retropharyngeal space.

Liver: Lesion is located inside or touches the liver parenchyma.

Spine or Paraspinal: Lesion is located within vertebral body or within 1cm of a vertebral body, pedicle or posterior elements.

Bone: Lesion is located within a bony structure (excluding spine).

Adrenal Gland/Pelvic Metastases: Lesion arises within the adrenal gland or within the true pelvis or inguinal nodes.

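### Section 6.3's airway list omits the left lower lobe bronchus and states the 2 cm margin twice, so the class and Table 2 dose of some lung lesions are inconsistent or unclear

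*Protocol*

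**What the plan says.** Protocol section 6.3 assigns every lesion to one of the seven locations in Table 2. Two of them are lung classes.

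- **Lung Peripheral:** "The lesion is outside the proximal bronchial tree as defined as within 2cm in all directions around the carina". The airway list then covers the main and upper lobe bronchi on both sides, the intermedius and the right middle lobe bronchus, and closes with "lingular bronchus and right lower lobe bronchi". A further sentence reads "The lesion does not the mediastinal or pericardial pleura"; its verb is absent in the text at hand.
- **Lung Central:** "The lesion is within 2cm of the proximal bronchial tree". There is no pleural condition here.

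The class has two consequences.

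- **Dose (section 6.1):** "Patients will receive the radiation therapy dose specified in" Table 2 for the site. Table 2 gives 45 Gy in 3 fractions for peripheral and 50 Gy in 5 for central lung lesions. The accepted variation is 40 Gy in 5 for both.
- **Imaging (section 6.2):** "IV contrast is required for central lung lesions and liver metastases", while for other sites "the use of IV contrast is encouraged and left to the discretion of the treating radiation oncologist".

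Section 6.1 also says: "No more than one lung lesion may be treated".

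**The concern.** A rule that selects an ablative schedule should give one answer for each lesion and the same answer on both sides of the chest. Section 6.3 falls short in two separate ways.

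First, the list treats left and right alike for main and upper lobe bronchi but not for lower lobe bronchi. A lesion lying against the left lower lobe bronchus can be peripheral when the matching right-sided lesion is central.

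Second, the 2 cm distance is part of what the proximal bronchial tree means in the peripheral definition, and it is then added to that same term in the central definition. Two planners can read one lesion into different classes and both be following the text.

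What is at stake is the starting schedule and whether IV contrast is mandatory. Section 2.1 gives uniformity as the reason for adopting external dose guidelines, and an uneven class rule works against that aim.

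**Working it through.** There is no plan figure to reproduce. The check applies the definitions to a distance and then compares the doses.

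**Step 1: the two definitions as sets.** Let *d* be the distance from a lesion to the nearest listed airway. The pleura sentence is set aside.

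| Reading | Peripheral | Central | Result |
|---|---|---|---|
| Margin counted once | *d* > 2 cm | *d* ≤ 2 cm | one class each |
| Literal, margin counted twice | *d* > 2 cm | *d* ≤ 2 + 2 = 4 cm | both classes for 2 < *d* ≤ 4 cm |

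**Step 2: the missing airway.** Take a lesion close to the left lower lobe bronchus with *d* > 2 cm for every listed airway.

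- Margin counted once: it is peripheral. The mirror-image lesion beside the right lower lobe bronchus has *d* ≤ 2 cm and is central.
- Literal reading: it meets both definitions if *d* ≤ 4 cm and only the peripheral one beyond that. The right-sided lesion is still central only.

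Neither reading treats the two sides alike. The stacked margin shrinks the left-sided gap, but replaces a clear class with an ambiguous one.

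**Step 3: what the class changes (Table 2).**

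- Peripheral: 45/3 = 15 Gy per fraction.
- Central: 50/5 = 10 Gy per fraction.

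**Step 4: does the peripheral schedule allow a larger airway dose effect?** The inputs are the trachea and ipsilateral bronchus limits in Appendix II, Table 3.0 (3 fractions) and Table 4.0 (5 fractions). The formula is BED = D × (1 + d_f/(α/β)), where D is total dose and d_f is dose per fraction. The protocol gives no α/β, so 2 to 5 Gy is assumed.

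| α/β (Gy) | <0.03 cc: 30 Gy/3 vs 40 Gy/5 | <5 cc: 25.8 Gy/3 vs 32 Gy/5 |
|---|---|---|
| 2 | 180 vs 200 (−10.0%) | 136.7 vs 134.4 (+1.7%) |
| 3 | 130 vs 146.7 (−11.4%) | 99.8 vs 100.3 (−0.5%) |
| 5 | 90 vs 104 (−13.5%) | 70.2 vs 73.0 (−3.8%) |

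For example, at α/β = 3 and 30 Gy in 3: 30 × (1 + 10/3) = 130. The 3-fraction caps are tighter at the small volume and about equal at 5 cc.

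**Step 5: the pleura sentence.** If its verb means touch, a pleura-touching lesion is not peripheral, and it is not central either if it lies beyond the central distance (2 cm or 4 cm by reading). It would then have no lung class. This step depends on a word that cannot be read in the text at hand.

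**The case against.** The case against giving this weight is good in several respects.

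- **The literal 4 cm reading is strained.** One location per lesion implies exclusive classes, and a radiation oncologist may well count 2 cm once. That stands as a guess at intent. It removes the overlap, but it then leaves the left-sided omission at full strength.
- **The omission looks like a slip.** The plural ending in a list that elsewhere pairs right and left suggests dropped words. That is plausible and supports the fix, but the rule as written is still one-sided.
- **A reader might infer that the missing bronchus makes the classes non-complementary.** It does not. Both classes refer to the same list, so the omission moves the boundary on the left without opening a gap or overlap. The overlap comes only from the repeated margin.
- **A reader might infer that left-sided airways may be overdosed.** The document does not support this. The Table 2 dose is allowed only if normal tissue criteria are met, section 6.5 has one contour list for all lung lesions, and the Appendix II airway limits are not tied to the section 6.3 list. Step 4 shows no materially higher permitted effect.
- **A reader might infer that pleura-touching lesions definitely have no class.** That rests on a sentence whose verb may have been lost in text extraction, so it remains conditional.
- **Identical dosing was never guaranteed.** Section 2.1 allows physician-discretion reductions to pre-specified doses. But these apply when dosimetric criteria cannot be met; they do not say which class a lesion starts in.

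**Conclusion.** The point holds as a minor correction for consistent dose assignment. The left lower lobe bronchus is absent from the list, so a lesion near it but more than 2 cm from every listed airway can start at 15 rather than 10 Gy per fraction and lose the contrast mandate, though not necessarily the contrast. On a literal reading, lesions about 2 to 4 cm from a listed airway also fit both classes.

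The harm is small. The airway caps bind in either class and at most one lung lesion per patient is treated. Both lung rows share the 40 Gy in 5 variation and section 6.1's 30 Gy in 5 default, so dose is lost only where the 3-fraction limits fail but 50 Gy in 5 would have passed. The number of affected lesions is not given. No objective in section 3 and no stratum in section 8.2 uses lung class, so no statistical figure changes.

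The distances follow from the text; the BED comparison depends on the assumed α/β of 2 to 5 Gy.

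**What to change.** In section 6.3:

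1. Extend the end of the airway list to the right and left lower lobe bronchi.
2. Let the proximal bronchial tree mean the listed airways themselves, and state the 2 cm margin once, measured from them.
3. Define Lung Central as within 2 cm of those airways, and Lung Peripheral as every lung lesion that is not central.
4. Complete the pleura sentence. If it means touch, place lesions touching the mediastinal or pericardial pleura in Lung Central.

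Items 2 and 3 make the classes exclusive and exhaustive; item 1 makes them symmetric. The cost is a wording amendment, with no change to endpoints, sample size or analysis.

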6.4 Target Delineation and Treatment Planning

The gross tumor volume (GTV) will be contoured in the appropriate CT window. Rigid PET-CT/MRI fusion is allowed to assist in target delineation when necessary.

No clinical target volume (CTV) expansion is allowed. GTV=CTV.

For non-fiducial based tracking treatments, an internal target volume (ITV) must be generated for motion susceptible targets. The expiratory and inspiratory phase scans (Phase 0 and 50) from a 4D-CT are suggested for defining the ITV. MIP reconstructed images should be used with caution because lung and MIP reconstructions may erroneously generate an ITV when breathing is irregular or when lesions abut soft tissue structures.

A 3-5mm uniform expansion will be added to generate the planning target volume (PTV). 95% of the prescribed dose should encompass 100% of the PTV.

6.5 Organs at Risk (OAR)

OAR must be contoured. The specific OAR to be contoured will depend on the location of lesion being treated.

Lung Central/Lung Peripheral/Mediastinal/Cervical Lymph Node metastases:

The proximal tracheobronchial tree, lungs, left/right/combined, heart, esophagus, spinal cord, chest wall, brachial plexus (when at risk), skin, liver, larynx, stomach will be contoured.

Abdominal-pelvic metastases (liver, adrenal, lymph nodes):

The stomach, duodenum, spinal cord, kidneys, large and small bowel, rectum, bladder, lungs, and cauda will be contoured.

Spinal Metastases:

All spine target volumes will be contoured per the international spine radiosurgery consensus guidelines for target delineation. A partial spinal cord volume 6mm above and below the target region will be contoured. Additional OAR will be based on the spine level.

6.6 Dose Limits and DVH Criteria

See Appendix II.

6.7 Evaluation of Targeted Lesions

Targeted lesions will be evaluated on 3 month interval scans or scans procured for clinical progression. Evaluated lesions will be described as follows:

Complete Response (CR): Disappearance of target lesion.

Partial Response (PR): At least 30% decrease in the sum of the diameters of the target lesions using the baseline sum of diameters.

Progressive Disease (PD): At least 20% increase in the sum of the diameters of target lesions, taking as reference the smallest sum on study (this includes the baseline sum if that is the smallest on study). In addition to the relative increase of 20%, the sum must also demonstrate an absolute increase of at least 5 mm (0.5 cm).

Stable Disease (SD): Neither sufficient shrinkage to qualify for PR nor sufficient increase to qualify for PD, taking as reference the smallest sum diameters while on study.

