2.0 PROPOSED TRIAL RATIONALE

Anti-PD-1 antibodies have demonstrated activity in the treatment of lung cancer. Opdivo was approved in February of 2015 by the FDA for patients with metastatic squamous NSCLC with progression on or after platinum based therapy. In the open-label trial, patients were randomized to receive OPDIVO (n=135) administered at 3mg/kg every 2 weeks. Median survival was improved to 9.2 months compared to 6 months in patients receiving docetaxel (n=137) 75mg/m² every 3 weeks, p=0.00025. Median progression free survival was slightly improved to 3.5 months compared to 2.8 months but 1 year overall survival was improved to 42% compared to 24% (36).

We expect that improvements in local control, increased immunogenic response and abscopal effect seen with combined modality treatment will result in improved local control, progression free survival and resultant significant increases in overall survival beyond 3 months. We propose a pilot/phase II study to assess the safety and efficacy of combination immunotherapy and stereotactic ablative radiation therapy (I-SABR).

Treatment will be a sequential combination treatment of SABR/SBRT and immunotherapy to assess the safety and feasibility of treatment. SABR/SBRT will be administered in 3-5 daily treatments followed by immunotherapy following the conclusion of SABR/SBRT. This approach will take advantage of the transient increase in antigen availability, increased antigen presentation and upregulation of PD-1 by tumor cells following ablative radiation therapy. After an interim safety analysis, the study will continue to the phase II portion where overall survival, progression free survival and response rate will be the primary and secondary end points. For reference, outcomes will be compared to the immunotherapy arms of checkmate 057 and Keynote 042 trials.

Several trials examining combination I-SABR are currently underway. A table of selected studies is included in [Table 1](#).

Study (Institution)	SABR Target	Dose (Gy/Fractionation)	Immunotherapy Agent	Sequence
NCT02239900 (MD Anderson Cancer Center)	Liver Lung Adrenal	50/4 60/10	Ipilimumab	Concurrent/Sequential
NCT01862900 (Chiles Research Institute)	Lung Liver	15/1 201/1	Anti-OX40	Concurrent
NCT01769222 (Stanford University)	Any	20/2	Ipilimumab	Concurrent
NCT02298946 (NIH/NCI)	Liver	8/1 24/3	PD-1 Inhibitor	Sequential

Table 1. List of selected ongoing I-SABR studies

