6.8 Evaluation of Non-Target Lesions

Complete Response (CR): Disappearance of all non-target lesions and normalization of tumor All lymph nodes must be non-pathological in size (<10 mm [<1 cm] short axis).

Progressive Disease (PD): Unequivocal progression of existing non-target lesions. It must be representative of overall disease status change, not a single lesion increase in size.

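### Section 6.7 gives target lymph nodes no size rule for complete response, so an irradiated node that shrinks below 10 mm but stays visible is scored PR or SD, not CR

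*Protocol*

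**What the plan says.** Section 6.7 of the protocol sets the response categories for irradiated lesions:

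- CR: "Complete Response (CR): Disappearance of target lesion".
- PR: "At least 30% decrease in the sum of the diameters of the target lesions using the baseline sum of diameters".
- SD is the residual category: "Neither sufficient shrinkage to qualify for PR nor sufficient increase to qualify for PD".

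The section does not mention lymph nodes and does not say whether a node's long or short axis counts as its diameter.

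Nodes are among the planned targets. Table 2 in section 6.1 has a row for "Mediastinal/Cervical Node". Section 6.3 defines that location ("The lesion arises in the anatomic mediastinum or cervical lymph node levels I-VI or retropharyngeal space") and places inguinal nodes in the adrenal/pelvic location. Neither section sets a minimum node size.

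The only nodal size rule is in section 6.8, headed for non-target lesions: "All lymph nodes must be non-pathological in size (<10 mm [<1 cm] short axis".

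Section 2.0 says that in phase II "overall survival, progression free survival and response rate will be the primary and secondary end points". RECIST 1.1 is cited in inclusion criterion 5 (section 5.1, repeated in Addendum 2), which concerns having a measurable lesion.

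**The concern.** The 10 mm short-axis rule in section 6.8 shows that the authors regard a node of normal size as no longer pathological. Section 6.7 does not carry that rule over to irradiated nodes, where CR requires disappearance. A node that has returned to normal size and can still be seen on the scan is therefore denied CR and falls to whatever the percentage change in the sum gives.

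The unstated axis adds a second problem: two readers can follow 6.7 faithfully and put the same node in different categories.

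At stake are the CR/PR/SD split and, where the result is SD rather than CR or PR, the response rate. The literal rule errs in one direction, by understating response in patients whose nodes were irradiated.

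**Working it through.** The protocol gives no figure to reproduce, so the check applies its rules to example nodes. All node sizes below are illustrative assumptions in mm. The rules are the protocol's:

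- CR only if the lesion has disappeared (6.7).
- PR if (baseline sum − current sum) / baseline sum ≥ 30% (6.7).
- SD if neither PR nor PD (6.7).
- Normal node size: short axis < 10 mm (6.8).

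**Lone node, short axis, still visible, now under 10 mm**

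| Baseline → now | Fall | Category under 6.7 |
|---|---|---|
| 20 → 8 | 12/20 = 60.0% | PR |
| 16 → 9 | 7/16 = 43.8% | PR |
| 15 → 9.9 | 5.1/15 = 34.0% | PR |
| 13 → 9 | 4/13 = 30.8% | PR |
| 14 → 9.9 | 4.1/14 = 29.3% | SD |
| 12 → 9 | 3/12 = 25.0% | SD |
| 11 → 9 | 2/11 = 18.2% | SD |

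None is CR. A fall to just under 10 mm misses PR when baseline is below 10/0.70 = 14.3 mm. For a fall to 9 mm the limit is 9/0.70 = 12.9 mm. Above 14.3 mm a lone node measured on its short axis changes only between CR and PR.

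**Sums of several lesions** (section 5.1 requires at least two SBRT-amenable lesions)

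- Node 15 → 9, and a 30 mm non-nodal lesion that disappears: 45 → 9, a fall of 36/45 = 80%. This is PR, although the only residue is a normal-size node.
- Nodes 15 → 9.9 and 11 → 9.9: 26 → 19.8, a fall of 6.2/26 = 23.8%. This is SD, although both nodes are of normal size. A node above 14.3 mm has been drawn into SD by the sum.
- Node 20 → 9, with a 30 mm lesion unchanged: 50 → 39, a fall of 11/50 = 22.0%. This is SD, but a nodal rule would not change the patient's category because the other lesion is still present. It counts as a misclassification only if CR is read lesion by lesion, which the singular wording of the CR line allows and the sum-based PR line does not.

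**Axis not stated**

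Take a node of 22 × 13 mm that becomes 16 × 9 mm. On the long axis the fall is 6/22 = 27.3%, which is SD. On the short axis it is 4/13 = 30.8%, which is PR. Under the 6.8 threshold the node is of normal size. One node can thus yield three answers.

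The same gap reaches the PD rule (at least 20% and at least 5 mm). A long axis of 20 → 25 is +25% and +5 mm, so PD. A short axis of 12 → 15 is +25% but only +3 mm, so not PD.

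**The case against.** The strongest reply is that section 6.7 is an abbreviated RECIST 1.1, as inclusion criterion 5 suggests by tying measurability under that standard to response assessment. That shows the likely intent and makes this look like a drafting slip. It does not settle the matter, because nothing in the protocol says that RECIST 1.1 governs 6.7 or overrides its written rules.

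It can also be said that the sentence in 6.8 refers to all lymph nodes. Its place inside the CR definition for non-target lesions argues against extending it to irradiated ones, although words appear to be missing just before it.

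Measurement conventions may be left to an SAP or imaging instructions, and the axis alone might fall there. The CR definition does not: the protocol fixes it here.

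Several stronger readings are tempting, and the documents do not support them:

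- **An irradiated node can never be CR.** This is true only of nodes that stay visible. A node that disappears is CR under 6.7. The protocol does not say how often treated nodes remain visible.
- **The same node would be CR if it had not been irradiated.** Section 6.8 also opens by requiring all non-target lesions to disappear, and it needs every one of them to resolve. A contrast of 0% CR against 100% would come from reading 6.7 strictly and 6.8 generously.
- **A known share of nodes is scored SD.** Any such share depends on assumed sizes. For lone nodes with final short axis uniform on 5–9.9 mm, it is about 25% for baselines uniform on 10–15 mm, 12% for 10–20 mm and 0% for 15–25 mm.
- **The main conclusions are threatened.** Response rate is named as an end point only in section 2.0. It is absent from the objectives in 3.1 and 3.2 and from the analyses listed in 5.3. Section 2.0 also plans comparison of outcomes with external trial arms without naming response rate. Understating response could not by itself create a false claim of benefit.

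**Conclusion.** The point holds as a minor flaw in a stated rule. Section 6.7 scores an irradiated node that is below 10 mm but visible as PR or SD, although the protocol's own nodal threshold would call it non-pathological. For a lone node on the short axis, SD needs a baseline below about 14.3 mm. For larger nodes it needs a sum with other lesions or use of the long axis.

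The consequence is an understated depth of response and, in some patients, an understated response rate. Overall survival is unaffected. Progression-free survival and local control depend on progression, so CR versus PR does not alter them. The unstated axis could in principle change a PD call, as the last example shows, but the point does not rest on that.

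The number of patients affected cannot be derived from the documents. It depends on how many have nodes irradiated, how large those nodes are, and how many remain visible after shrinking. The conclusion also assumes that readers apply 6.7 as written.

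**What to change.** In section 6.7, replace the CR line with: *Disappearance of all non-nodal target lesions; any target lymph node must be <10 mm in short axis.* Then add: *For target lymph nodes the short axis is the diameter entered in the sum.* This extends to irradiated nodes the threshold already in 6.8.

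Alternatively, state that response is scored by RECIST 1.1 in full, consistent with inclusion criterion 5.

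Either change needs only a sentence or two and no new scans or patients. The small cost is that nodes already recorded on the long axis would have to be re-measured on existing images.

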3.2 Secondary Objectives

The secondary objectives of the study are

1. To determine the progression free survival measured from time of enrollment to first evidence of progressive disease and evaluated 3 months after treatment initiation.
2. To determine the local control measured from time of enrollment to first evidence of progressive disease at the treatment site and evaluated 3 months after treatment initiation
3. To determine the incidence of grade ≥ 3 , pneumonitis 6 months of completing SBRT
4. To determine the influence of number of metastatic sites on OS, and PFS.

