4.1 STUDY DESIGN AND DURATION

This is a combination single arm pilot/Phase II study of combination I-SABR for metastatic NSCLC. Treatment safety and feasibility will be assessed in the initial pilot phase and oncologic outcomes will be assessed in the second phase.

After screening, patients will receive 3-5 fractions of SBRT/SABR to up to 3 metastatic sites in addition to the primary tumor. Following the conclusion of SBRT/SABR, patients will receive Immunotherapy therapy at standard dosing until disease progression or discontinuation of treatment due to toxicity or patient choice (Figure 1).

Tumor assessment will be performed prior to SABR initiation and every 3 months or for clinical disease progression.

Figure 1: Sample Patient Treatment and Follow-Up Timeline

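### Section 6.7 scores progression on the pooled sum of targeted lesions while local control is an event at the treated site, so one failing site among several can be masked

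*Protocol*

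**What the plan says.** Four parts of the protocol bear on this.

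- **Endpoint.** Section 3.2, item 2: "To determine the local control measured from time of enrollment to first evidence of progressive disease at the treatment site". It is to be evaluated 3 months after treatment starts.
- **Rule for targeted lesions.** Section 6.7 defines progression as "At least 20% increase in the sum of the diameters of target lesions, taking as reference the smallest sum on study", with a further condition that the sum rise by at least 5 mm. Partial response is "At least 30% decrease in the sum of the diameters of the target lesions using the baseline sum of diameters". Stable disease is whatever lies between. Only complete response is worded for a single lesion.
- **Rule for other lesions.** Section 6.8 gives two categories. Complete response is "Disappearance of all non-target lesions and normalization of tumor" (the sentence breaks off there in the text available). Progression must be unequivocal and must reflect overall disease, so growth of one lesion does not count. No partial or stable category appears.
- **Number of sites.** Section 4.1 allows "3-5 fractions of SBRT/SABR to up to 3 metastatic sites in addition to the primary tumor", so at most four. Section 5.1 requires at least two lesions amenable to SBRT.

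Section 2.0 says that "overall survival, progression free survival and response rate will be the primary and secondary end points" and plans comparison with the immunotherapy arms of other trials. It also expects "improvements in local control, increased immunogenic response and abscopal effect seen with combined modality treatment" to improve outcome. Section 3 lists neither response rate nor abscopal response as an objective.

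**The concern.** Local control asks whether each irradiated site stays controlled. The only numerical progression rule given for targeted lesions adds the sites together, so shrinkage at well-controlled sites offsets growth at a failing one. A patient with a clear failure at one site can be classed as stable, or even as a partial responder, and counted as locally controlled.

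A second difficulty concerns the word target. Section 6.7 sits in the radiation chapter, and section 6.1 speaks of target selection when it means choosing lesions to irradiate. Yet the definitions are in RECIST form. If targeted lesions are the irradiated ones, unirradiated lesions fall under 6.8, where partial shrinkage has no category. The trial would then have no defined way to record a partial response outside the field, although an out-of-field effect is part of its rationale. The response rate named in 2.0 would be scored on lesions given ablative radiation.

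**Working it through.** The protocol gives no expected local control rate and no power figure that depends on this rule, so there is no stated figure to reproduce. The check applies the 6.7 thresholds directly.

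**Inputs from the protocol.** Progression: sum up at least 20% and at least 5 mm from the smallest sum. Partial response: sum down at least 30% from baseline (both 6.7). Treated sites: up to 4 (4.1, 4.2).

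**Assumptions.** Treated lesions have equal baseline diameter d, baseline is the nadir, one lesion grows by a fraction g, and each other lesion shrinks by a fraction s. The protocol gives no diameters; 20 mm and 30 mm are used as examples.

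**Formula.** With k treated lesions the baseline sum is kd and the new sum is d(1+g) + (k−1)d(1−s). The relative change is [g − (k−1)s]/k. Setting this to at least 0.20 gives

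g ≥ 0.2k + (k−1)s.

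| Treated sites k | Others stable (s = 0) | Others shrink 30% (s = 0.3) |
|---|---|---|
| 2 | 0.4 + 0 = 40% | 0.4 + 0.3 = 70% |
| 3 | 0.6 + 0 = 60% | 0.6 + 0.6 = 120% |
| 4 | 0.8 + 0 = 80% | 0.8 + 0.9 = 170% |

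For two or more lesions of 20 or 30 mm the 20% condition governs the sum (for example 0.2 × 2 × 20 = 8 mm, above 5 mm). Applied to one lesion alone, the same rule is met at +6 mm (20%) for a 30 mm lesion and at +5 mm (25%) for a 20 mm lesion, whatever the other sites do.

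**Worked cases, 30 mm lesions.**

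| Diameters at scan (mm) | Sum (mm) | Change | Read from 6.7 | Growing site alone |
|---|---|---|---|---|
| 40, 20 | 60 → 60 | 0% | stable | +33%, progression |
| 45, 20, 20, 20 | 120 → 105 | −12.5% | stable | +50%, progression |
| 50, 30, 30, 30 | 120 → 140 | +16.7% | stable | +67%, progression |
| 37.5, 15, 15, 15 | 120 → 82.5 | −31.25% | partial response | +25%, progression |

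**Where masking is smaller.** With k = 1 the formula gives 20%, so there is none. It also weakens once the nadir has fallen. If three of four 30 mm lesions have already halved, the nadir is 30 + 15 + 15 + 15 = 75 mm, progression needs 75 × 1.2 = 90 mm, and the failing lesion must reach 45 mm, which is +50%. If the same halving is first seen on the scan that shows the growth, it must grow 0.8 + 3 × 0.5 = 230%. Scans are every 3 months (4.1) and local control is evaluated at 3 months (3.2), so the first scheduled scan, where baseline is still the nadir, is about the one that matters most.

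**Direction.** If the sum rises 20% above an earlier scan, at least one lesion has risen 20% above its size on that scan, and hence above its own nadir. Pooling therefore hides or delays failures. The exception comes from the 5 mm condition: four 10 mm lesions each reaching 12 mm give 40 → 48 mm (+20%, +8 mm), progression on the sum although none has grown 5 mm.

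**Unequal lesions.** If the failing lesion makes up a share w of the baseline sum and the others are stable, it must grow 0.2/w: 25% for w = 0.8, 200% for w = 0.1. Small failing lesions are masked most.

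**The case against.** The strongest reply is that section 3.2 defines the local control event itself, at the treatment site, and nothing says it must be read from the sum in 6.7. Complete response in 6.7 is worded for one lesion, and a per-site rule might stand in a statistical analysis plan that is not shown. This makes the bias conditional. It does not remove the mismatch: the protocol states one numerical progression rule for targeted lesions, no per-site rule, and an endpoint that needs one.

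A second reply is that 6.7 may mean RECIST target lesions. The definitions are in RECIST form, 6.8 refers to overall disease status, and section 5.1, criterion 5, asks for a RECIST-measurable lesion for response assessment, with an FDG-avid lesion as the alternative. On that reading measurable unirradiated lesions could enter the sum, and partial shrinkage outside the field could count. The section context favours the irradiated reading but does not settle it. On either reading there is no per-site rule and irradiated lesions contribute to response.

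Three stronger inferences are not supported:

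- *That no abscopal response can be recorded.* Disappearance of all non-target lesions is a complete response under 6.8. Only a partial response, or clearance of some lesions, lacks a category. The broken sentence in 6.8 also calls for caution, since text may have been lost in reading the file.
- *That a listed objective depends on out-of-field response.* The phase II primary objective is overall survival, which these rules do not touch. Response rate appears as an endpoint only in section 2.0.
- *That a particular response rate would arise from radiation alone.* The protocol gives no figure from which to derive one.

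**Conclusion.** The point holds in a limited form. Section 6.7 fixes progression on a pooled sum that does not match the site-level local control endpoint in 3.2. With two to four treated sites, a site that meets the 20% and 5 mm thresholds by itself can be read as stable disease or partial response. The growth needed for detection rises from 20–25% to 40–80% when the other sites are stable, and to 70–170% when they shrink 30%. These figures assume equal lesions and baseline as nadir. How many patients would be affected cannot be derived from the protocol, because it gives neither the distribution of treated sites nor how often lesions behave discordantly.

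The upward bias applies if local control is read from 6.7. The meaning of target is unsettled. On the likelier reading a partial out-of-field response has no category. On either reading the response rate in 2.0 includes the direct effect of radiation, unless irradiated lesions are kept out of the target set, which the text does not say. This should be corrected, but it concerns a secondary endpoint and a rate named in the rationale, not the primary analysis.

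**What to change.** 1. In 6.7 and 6.8, state whether target means irradiated lesions or RECIST target lesions, and use one term throughout.
2. For local control, apply the 20% and 5 mm rule to each irradiated lesion against its own nadir. Date the patient's local failure at the first lesion to fail. Section 5.1, criterion 5, admits patients followed by SUV Max, so lesions assessed only by PET need a matching per-lesion rule.
3. For measurable unirradiated lesions, tabulate complete response, partial response, stable disease and progression separately, among patients who have at least one. Present this as descriptive. It should not be the rate set against immunotherapy-alone trial arms, because patients with a measurable lesion left after up to four sites are treated are likely to have more disease than those arms as a whole.

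The cost is wording and some extra per-lesion tabulation from scans already planned. Reported local control will be somewhat less favourable, and the out-of-field table will cover only part of the cohort.
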